4 INVESTIGATIONAL PLAN

4.1 Overall Study Design and Plan

This is a 52-week, Phase 2a, randomized, double-blind, parallel-group, placebo-controlled, multicenter proof-of concept study to evaluate the safety and efficacy of elezanumab in subjects with acute ischemic stroke.

The schematic of the study is shown in [Figure 1](#). Further details regarding study procedures are located in the Operations Manual ([Appendix F](#)). Also see Section 5 for information regarding eligibility criteria.

The Screening Period is up to 24 hours since "last known normal" (the time before hospital arrival at which the subject was last known to be without the signs and symptoms of the current stroke or at his or her baseline state of health). Treatment with IV tPA and/or EVT will be allowed before randomization and will be recorded as a concomitant therapy.

[figure not shown]
Randomization will be stratified by IV tPA use (yes/no), by EVT use (yes/no), and by time since last known normal (≤ 11 hours or > 11 hours). The proportion of subjects enrolled who have EVT is targeted to be up to approximately 50% of the study population. A target of approximately 25% to 50% of subjects may be randomized within the time window of ≤ 11 hours since last known normal. Lastly, the proportion of subjects who enroll > 80 to 90 years of age is targeted to be up to approximately 30% of the study population. Eligible subjects will be randomized in a 1:1 ratio to receive either elezanumab 1800 mg or placebo as an IV infusion.

Administration of blinded study drug must be initiated as soon as possible but no later than 6 hours after randomization and done every 4 weeks thereafter through Week 48 for a total of 13 doses. The final double-blind Treatment Period study visit will be at Week 52. Subjects will have 2 post-treatment follow-up visits at 12 and 24 weeks after last dose of study drug, and a final follow-up phone call 39 weeks (5 half-lives) after last dose of study drug. All follow-up visits beginning at Week 4 during the Treatment Period and Follow-up Period will be allowed a window of \pm 7 days, and study procedures may be conducted over a period of 2 days. Unblinded safety data will be reviewed by an external DMC per the DMC Charter.

Final efficacy analyses will be performed after the last subject completes the Week 52 visit. Final safety analyses will be performed following completion of the post-treatment period and database lock.

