4.2 Discussion of Study Design

Choice of Control Group

Approximately 120 subjects will be randomized to elezanumab 1800 mg or placebo in a 1:1 ratio. Use of placebo as a control is appropriate since participation in the study does not preclude subjects from receiving standard-of-care treatment for acute ischemic stroke including thrombolytic therapy and EVT.

Appropriateness of Measurements

Standard clinical and laboratory procedures will be utilized in this study. All patient-reported outcome (PRO) and clinician-measured scales are standard for assessing stroke severity and recovery in subjects with acute ischemic stroke. All clinical and laboratory procedures in this study are standard and generally accepted.

Suitability of Subject Population

This study will enroll subjects with acute ischemic stroke with an NIHSS total score of 7 to 21, inclusive, who are expected to have residual functional impairment following recovery after standard-of-care

treatment, and thus have the capacity to show a treatment effect in this initial proof-of-concept study. Subjects with milder stroke (as determined by NIHSS score or imaging) may experience notable spontaneous recovery, while subjects with more profound stroke have substantially increased risk of death and permanent disability and may be more likely to discontinue prematurely.

Inclusion of subjects who were treated with IV tPA and/or EVT will allow for assessment of the safety and efficacy of elezumab in a patient population more aligned with current standard of care for acute ischemic stroke. To maintain the ability to detect a potential treatment effect, subjects treated with IV tPA and/or EVT will be required to have an NIHSS total score of 7 to 21, inclusive, at least 1 hour after completion of the treatment(s). From a safety perspective, there are no expected pharmacokinetic or pharmacodynamic interaction between elezumab and IV tPA or EVT. Additionally, subjects are required to have no evidence of intracranial hemorrhage to minimize risk to subjects in the study.

Timing and Duration of Treatment

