7.7 Sample Size Determination

The primary efficacy endpoint is the monthly-adjusted, model-based AUC of the NIHSS total score during the Treatment Period. Approximately [REDACTED] subjects will be randomized to elezanumab [REDACTED] mg or placebo in a [REDACTED] ratio. Assuming a true difference in AUC of [REDACTED], this sample size is sufficient to show a [REDACTED] difference in AUC between treatment and placebo with a posterior probability greater than [REDACTED]%. This sample size was calculated based on simulations and included a [REDACTED] % mortality rate for the population under [REDACTED] years of age, [REDACTED] % mortality rate for the population greater than or equal to [REDACTED] years of age, and an additional [REDACTED] % dropout rate.

The number and proportion of missing assessments (due to missed visits or study drug discontinuation) will be monitored on an ongoing basis and, if the proportion of missing assessments is higher than planned, additional subjects may be added.

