8.2 Handling of Missing Data

Missing data will be imputed using the following methods for the efficacy analyses:

- Non-Responder Imputation (NRI): the NRI analysis will categorize any subject who does not have evaluation during a specific visit window as a non-responder for that visit. Unless otherwise noted, this will be the primary approach for accounting for missing data in responder analyses.
- Generalized linear mixed model (GLMM): The model will include a logit link function to compare the probability of having responder between treatment groups of each visit of Day 2-4, Week 4, Week 8, Week 12, Week 24, Week 36, Week 52, and will include baseline NIHSS as a covariate and time from last known normal and initiation of first dose (≤ 12 hours, > 12 hours), tPA use (Y/N), EVT use (Y/N), visit, and treatment group as fixed effects. An unstructured variance covariance matrix will be used. The compound symmetry variance covariance matrix will be used if the model does not converge with unstructured matrix. The GLMM model relies on a missing at random (MAR) assumption.
- As Observed (AO): The AO analysis will not impute values for missing evaluations, and thus a subject who does not have an evaluation on a scheduled visit will be excluded from the AO analysis for that visit. AO will include all values collected in the study.
- MMRM: The repeated measures analysis will be conducted using a mixed model including observed measurements at all visits. The mixed model includes the categorical fixed effects of treatment, visit and treatment-by-visit interaction, main stratification factors at randomization, and the continuous fixed covariates of baseline measurement, unless otherwise noted. An unstructured variance-covariance matrix will be used; if the model does not converge, then a compound symmetry variance-covariance matrix will be used. Denominator degrees of freedom will be computed using the Kenward-Roger method. Parameter estimation is based on the assumption of data being missing at random and using the method of restrictive maximum likelihood. MMRM will be the primary approach in the analysis of continuous

variables unless otherwise noted. The MMRM model relies on a missing at random (MAR) assumption.

For all analyses related to the mRS, if a subject has a value of 6 (dead), this will be carried forward to future visits in the analysis. This will be applied to all mRS analyses, including the responder analysis as observed.

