8.3.3 Primary Efficacy Analysis

The primary efficacy analysis will be based on the monthly-adjusted area under the curve (AUC) derived from an MMRM. The dependent variable is the NIHSS total score during the Treatment Period. The model will include the stratification factors of tPA use (Y/N), EVT use (Y/N), time since last known normal (≤ 12 hours, > 12 hours based on time between last known normal and study drug initiation), main effects of treatment group and visit, and the treatment-by-visit interaction. The REPEATED statement will be used for visit with blocks in the covariance matrix identified by subject nested within treatment group. The unstructured covariance structure will be used to estimate the within subject variance-covariance; if the model does not converge with this variance-covariance structure, then compound symmetry will be used.

The monthly-adjusted AUC of NIHSS total score for each treatment group will be obtained using the trapezoidal method where i = treatment group (placebo, elezanumab) and j = visit during the Treatment Period {Day 1, Day 2-4, Week 4, Week 8, Week 12, Week 24, Week 36, Week 52}:

$$AUC_i = \frac{1}{13} \sum_{j=Stabil.(Day 2-4)}^{Week 52} \frac{(Week Number_j - Week Number_{j-1})}{4} \frac{1}{2} (LS Mean_{i,j} + LS Mean_{i,j-1})$$

The AUC for each treatment group, as well as the difference in AUCs (placebo minus elezanumab) and their respective standard errors and confidence intervals will be presented.

The posterior probability that the difference in AUCs being greater than 0.6 based on the observed data will be presented.

The attributes of the estimand corresponding to the primary efficacy objective are summarized in [Table 1](#).

Table 1. Summary of the Estimand Attributes Corresponding to the Primary Efficacy Objective

Estimand Label	Attributes of the Estimand					Statistical Summary
	Treatment	Endpoint	Population	Handling of Intercurrent Events		
NIHSS total score AUC	Elezanumab 1800 mg or placebo IV Q4W (13 doses)	NIHSS total score at each visit	FAS	Missing data due to intercurrent events (e.g., premature discontinuation of study drug, lost to follow-up, death, COVID-19) will be handled using MMRM with MAR assumption	Difference in monthly-adjusted AUC between treatment groups	

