8.4 Secondary Efficacy Analyses

The point estimate of the responder rate, odds ratio, and corresponding 95% confidence intervals will be derived from a generalized linear mixed model (GLMM) with a logit link function to compare the probability of having responder between treatment groups of each visit of Week 4, Week 8, Week 12, Week 24, Week 36, Week 52. The model will include time from last known normal and initiation of first dose (≤ 12 hours, > 12 hours), tPA use (Y/N), EVT use (Y/N), visit, treatment group as fixed effects, and visit as the random effect by subject. An unstructured variance covariance matrix will be used. The compound symmetry variance covariance matrix will be used if the model does not converge with unstructured matrix.

[figure not shown]

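### Age is in neither the primary NIHSS model nor the visible mRS model, so a chance age imbalance between about 60 subjects per arm stays uncorrected and a little precision is lost

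*SAP*

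**What the plan says.** **Primary model.** SAP 8.3.3: "The model will include the stratification factors of tPA use (Y/N), EVT use (Y/N), time since last known normal", the last split at 12 hours to study drug initiation, plus "main effects of treatment group and visit, and the treatment-by-visit interaction". Day 1 is one of the eight response visits. Protocol 7.3 (Primary Efficacy Analysis) lists the same terms. Age is not among them.

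**mRS model.** SAP 8.4 names time from last known normal and "tPA use (Y/N), EVT use (Y/N), visit, treatment group as fixed effects, and visit as the random effect by subject". The general GLMM in SAP 8.2 differs in that it "will include baseline NIHSS as a covariate and time from last known normal and initiation of first dose", but it does not name age either.

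**Randomisation.** Protocol 4.1: "Randomization will be stratified by IV tPA use (yes/no), by EVT use (yes/no), and by time since last known normal". Age is not a stratum.

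**Where age does appear.** Protocol 7.7 sizes the trial with one "mortality rate for the population under" a redacted age and another at or above it. Protocol 4.1 says "the proportion of subjects who enroll > 80 to 90 years of age is targeted to be up to approximately 30" per cent of the study population. Age is tabulated at baseline (SAP 7.1) and is a subgroup factor (Protocol 7.3, SAP 8.6). The subgroup fits are run in separate subsets, so they do not adjust the overall comparison. No age-adjusted sensitivity analysis is visible.

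**The concern.** The plan uses age to generate deaths in its sizing simulation and to limit recruitment, but not to estimate the treatment effect. Eligible age runs from 30 to 90. If age predicts outcome, arms that differ in age by chance will differ in outcome for that reason, and neither visible model removes the difference.

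For mRS the link through mortality is direct: death scores 6, is carried forward (SAP 8.2) and cannot be a favourable outcome. For NIHSS it is indirect. Deaths are missing data under MAR (SAP Table 1). MAR is conditional on what the model contains, and the variable that the sizing ties to death is outside it.

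The readouts are posterior probabilities against small fixed margins, 0.6 NIHSS points and 6.25 percentage points, with noninformative priors. Nothing in the prior dampens a chance shift, and an age adjustment added after unblinding would be post hoc.

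**Working it through.** **Inputs from the documents.** "Approximately 120 subjects will be randomized to elezanumab 1800 mg or placebo in a 1:1 ratio" (Protocol 4.2), so about 60 per arm. Margins 0.6 and 6.25% (Protocol 7.3). The planned sample size cannot be reproduced: the true AUC difference, posterior target, mortality rates, age cut and dropout rate are redacted, and no SD is given.

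**Assumed inputs.** Age SD 10 to 12 years; 0.03 to 0.10 NIHSS points per year on the AUC scale; log-odds of mRS 0 to 2 of -0.02 to -0.05 per year with 45% favourable; AUC SD 5 where needed. None of these is in the documents.

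**1. Size of a chance age imbalance.** SE = SD × √(2/60).
- SD 10: 1.83 years. SD 12: 2.19 years.
- Median absolute imbalance = 0.6745 × SE = 1.2 to 1.5 years.
- 95% range = ±1.96 × SE = ±3.6 to ±4.3 years.
- An imbalance of 2 years or more occurs in 27 to 36% of trials, and of 4 years or more in 3 to 7%.

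**2. Shift in the NIHSS AUC difference** = imbalance × slope.

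| Imbalance | Low slope, SD 10 | High slope, SD 12 |
|---|---|---|
| Typical | 1.23 × 0.03 = 0.04 | 1.48 × 0.10 = 0.15 |
| 95% extreme | 3.58 × 0.03 = 0.11 | 4.29 × 0.10 = 0.43 |

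**3. Shift in the mRS responder difference** at a 4.3-year imbalance: about 2.1, 3.1 and 5 points for log-odds of -0.02, -0.03 and -0.05 per year.

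**4. Cross-check on the share over 80.** With 30% over 80 in each arm, the SE of the between-arm difference is √(2 × 0.3 × 0.7/60) = 8.4 points. An imbalance of 10 points or more occurs in 27% of trials. If those over 80 score 1 to 4 points worse (assumed), a 10-point imbalance moves the AUC difference by 0.1 to 0.4.

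**5. What a shift does to the readout.** With AUC SD 5, SE = 5 × √(2/60) = 0.913. For an age-balanced difference of 1.2, P(difference > 0.6) = Φ(0.6/0.913) = 0.74. A shift of -0.3 gives Φ(0.3/0.913) = 0.63; a shift of +0.3 gives Φ(0.9/0.913) = 0.84.

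**6. Behaviour over repeated trials.** In 40,000 simulated trials with no drug effect, 30% over 80 and AUC SD 5, the unadjusted estimate averages about 0.00 and its 95% interval covers 95%. Among the 13.6% of trials in which placebo has at least 10 points more subjects over 80, the unadjusted difference averages 0.29 (old-young gap 2) or 0.41 (gap 3). With age in the model it averages 0.02 or 0.01.

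**7. Precision.** In the same simulations the SE falls from 0.915 to 0.902 (gap 2) or from 0.916 to 0.883 (gap 3). R² = gap² × 0.21/25 = 0.034 or 0.076, and 120/(1 - R²) = 124 or 130, a gain of 4 to 10 subjects. On the slope scale with AUC SD 5, the lowest inputs give R² = (0.03 × 10/5)² = 0.004, a gain of less than one subject.

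**8. Form of the age term.** Take a 4.3-year imbalance, a slope of 0.08 per year from Week 4, and no slope at Day 1 or Day 2-4. The AUC shift is -0.33 with no age term and 0 with age-by-visit. With age as a main effect only, it lies anywhere from -0.17 to -0.40 over one set of assumed covariances. In a further check with SD 5 and correlation 0.7 at all visits, it is -0.07. A main effect alone is unreliable because it forces one slope on Day 1, where entry limits NIHSS to 7 to 21, and on the recovery visits.

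**The case against.** The strongest reply is that this is not a flaw in validity. Chance age variation is already in the residual variance, and so in the SE and the posterior; step 6 confirms it. A reader might infer that both results are biased. The documents do not support that: any shift is conditional on the allocation that happens to arise.

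A reader might also take 0.43, about 70% of the 0.6 margin, as the expected size. It multiplies the 95% extreme by the larger assumed SD and the largest assumed slope. The typical figure is 0.04 to 0.15.

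The evidence that age matters is partial. The plan ties age to mortality, with the rates redacted, and not to NIHSS level among survivors. The limit on those over 80 is an approximate target. Being a subgroup factor shows nothing, since sex is on the same list.

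It is also tempting to say that the 6.25% comparison cannot be corrected for age. That goes too far. Part of SAP 8.4 is not shown, and Protocol 7.3 names no covariates for that posterior. An age-adjusted sensitivity analysis in withheld text cannot be excluded.

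On MAR, the unstructured model already conditions on each subject's observed NIHSS course, and adding age would not settle whether death should be treated as missing data.

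Finally, the study is exploratory with no formal tests, and an imbalance would show in the baseline tables. All of this stands as a limit on size and certainty. None of it is a reason to leave age out: seeing an imbalance is not adjusting for it, and a prespecified adjustment is cheap.

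**Conclusion.** The omission is certain for the primary MMRM and for the visible mRS GLMM. Its consequence is conditional imbalance in a single trial plus a modest loss of precision, not systematic error or faulty intervals. Under the assumed inputs, the AUC shift is about 0.04 to 0.15 for a typical imbalance and 0.11 to 0.43 at the 95% extreme, against 0.6. The mRS shift is about 2 to 5 points at a 4.3-year imbalance, against 6.25. The precision gain is worth roughly 4 to 10 subjects in the central cases. These sizes are illustrative because the documents give no age SD, outcome SD or age slope. For the 6.25% posterior, no conclusion is possible beyond the visible text. The change is worth making because it is nearly free and loses its value if left until after unblinding.

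**What to change.** - **SAP 8.3.3 and Protocol 7.3:** add continuous age and age-by-visit to the primary MMRM, and take LS means at the overall mean age in both arms. Do not add age as a main effect only while Day 1 is a response visit.
- **SAP 8.4:** add continuous age to the mRS GLMM. Reconcile SAP 8.2 and 8.4 on baseline NIHSS in that model at the same time.
- **Model behind the 6.25% posterior:** if it uses covariates, include age and obtain the responder difference by standardising over the observed covariates. A logistic age term changes the conditional odds ratio and does not by itself give a risk difference.
- **Pre-stroke mRS:** do not add it on this ground unless the score is recorded as data. Protocol 5.1 only requires confirmation that it was 0 to 2.

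**Cost.** SAP and protocol wording; age is already collected. The primary model gains about eight parameters (one age slope for each of eight visits) on top of an unstructured covariance with about 120 subjects. That adds a little to the risk of non-convergence and of falling back to compound symmetry.

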2.4 Sample Size Determination

The primary efficacy endpoint is the monthly-adjusted, model-based area under the curve (AUC) of the National Institutes of Health Stroke Scale (NIHSS) total score during the Treatment Period. Approximately █ subjects will be randomized to elezanumab █ mg or placebo in a █ ratio. Assuming the true difference in AUC is █, this sample size is sufficient to show a █ difference in AUC (with the elezanumab group having a lower, i.e., better, AUC) between treatment and placebo with a posterior probability of > █%. This sample size was calculated based on simulations and included a █% mortality rate for the population under █ years of age, █% mortality rate for the population greater than or equal to █ years of age, and an additional █% discontinuation rate.

The number and proportion of missing assessments (due to missed visits or study drug discontinuation) will be monitored on an ongoing basis and if the proportion of missing assessments is higher than planned, additional subjects may be randomized.

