The COVID-19 pandemic is interfering with the conduct of many ongoing trials, with potential impact on treatment duration and the collection, analysis and the interpretation of clinical trial data. Some protocol-specified visits in this clinical trial may be impacted due to COVID-19 infection or logistical restrictions during the pandemic. For example, some scheduled visits may be missed due to self-quarantine or local government restrictions on travel; some visits may also be delayed or canceled due to healthcare resource constraints during the pandemic. These missed visits will be recorded in the database. The probability of having missed visits and missing data due to COVID-19 infection or logistical restrictions related to the COVID-19 pandemic can be reasonably assumed to be unrelated to the unobserved values conditional on the observed data. Therefore, for the purpose of statistical analysis, it is reasonable to assume that these missing data are missing at random (MAR) and the statistical models that require MAR assumption are appropriate. In some cases, sensitivity analyses may be performed to assess the impact of missing data and the robustness of the conclusion.

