8.3.2 Handling of Missing Data for the Primary Efficacy Endpoint

Missing data will not be imputed for the primary analysis, which will be based on an MMRM model.

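### The primary NIHSS AUC treats death as missing at random, so it estimates a contrast as if nobody had died, and no visible AUC analysis counts death

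*SAP*

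**What the plan says.** SAP 8.3.3, Table 1, groups death with stopping study drug, loss to follow-up and COVID-19. Missing data from all of them are treated alike: "lost to follow-up, death, COVID-19) will be handled using MMRM with MAR assumption". SAP 8.3.2 adds: "Missing data will not be imputed for the primary analysis, which will be based on an MMRM model". No NIHSS value is assigned after death. The primary output follows from this model: each arm's AUC, "the difference in AUCs (placebo minus elezanumab) and their respective standard errors and confidence intervals will be presented", and the posterior probability that the difference exceeds 0.6.

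The only argument for MAR is in SAP 8.2 and concerns visits lost to COVID-19, for which "it is reasonable to assume that these missing data are missing at random (MAR". The same paragraph ends: "In some cases, sensitivity analyses may be performed to assess the impact of missing data and the robustness of the conclusion". It names no such analysis and does not mention death.

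Deaths were expected. SAP 2.4 and Protocol 7.7 build mortality into the sample-size simulation by age band ("mortality rate for the population greater than or equal to" a redacted age), with the rates redacted.

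Death is counted elsewhere. An mRS of 6 is carried forward (SAP 8.2), responder analyses default to non-response when a visit is missing, and the safety section tabulates deaths.

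**The concern.** Death differs from the other events in that row. A living patient who stops drug or misses a visit still has an NIHSS, and Protocol 5.6 asks sites to keep collecting it. After death no score exists. An MMRM under MAR then fills the gap implicitly from comparable same-arm patients. That is a hypothetical strategy for death. It can be a legitimate choice, but the reader should be told, and should be able to see what happens when deaths count.

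The AUC is the main proof-of-concept result. Apart from worsening recorded before death, it stays about the same whether mortality on elezanumab is double, equal to or half that on placebo. The visible continuous NIHSS outputs share the gap: the MMIAS repeat (no different handling of death is stated), the MMRM change from baseline, the as-observed distribution plot and the as-observed subgroup ANCOVA.

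**Working it through.** **The plan's own figure.** The sample size of about 120 came from simulations whose true difference, posterior probability, mortality and dropout are redacted, and no SD is visible. It cannot be reproduced.

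**Step 1: AUC weights (documents only).** Visits are at Weeks 0, 3/7 (Day 2-4 taken as Day 3), 4, 8, 12, 24, 36 and 52. Under the SAP trapezoid, an interior visit has weight (next week - previous week) / (2 x 52). The weights are 0.004, 0.038, 0.073, 0.077, 0.154, 0.231, 0.269 and 0.154, summing to 1. The weight W after a death is the sum over later visits:

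| Death between | W |
|---|---|
| Weeks 4 and 8 | 46/52 = 0.885 |
| Weeks 12 and 24 | 34/52 = 0.654 |
| Weeks 24 and 36 | 22/52 = 0.423 |
| Weeks 36 and 52 | 8/52 = 0.154 |

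**Step 2: effect of one death.** Let D be the score given to death and m the NIHSS that the MAR model implies for that patient. With 60 per arm, counting the death moves the arm AUC by W x (D - m) / 60. The number of excess deaths that moves the difference by 0.6 is 0.6 x 60 / (W x (D - m)). For deaths in Weeks 4-8 and m = 8 (assumed):

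- D = 21: 36 / (0.885 x 13) = 3.1
- D = 30: 36 / (0.885 x 22) = 1.8
- D = 42: 36 / (0.885 x 34) = 1.2

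For m from 6 to 18 the ranges are 2.7-13.6, 1.7-3.4 and 1.1-1.7.

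**Step 3: simulation (all inputs assumed).** 3,000 trials per scenario, 60 per arm, no NIHSS effect.

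- Means 13, 11, 8.5, 7.5, 7, 6.5, 6.2, 6; SD 4, 5.5, then 6; correlation 0.5 + 0.5 x 0.8^lag; scores kept within 0-42 (Day 1 within 7-21).
- Death risk multiplied by exp(0.10) per Day 2-4 NIHSS point. Timing 30/20/10/20/10/10% over the six intervals after Day 2-4.
- 10% random dropout among the living.
- Posterior = 1 - Phi((0.6 - d)/SE), flat prior. The composites and rank use multiple imputation for living dropouts only.

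Differences are placebo minus elezanumab; P is the mean posterior probability of exceeding 0.6; the rank column is the probability that elezanumab is better.

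| Mortality, placebo v elezanumab | MMRM (P) | Composite, D = 21/30/42 | P, composite | Rank |
|---|---|---|---|---|
| 10% v 20% | 0.00 (0.32) | -0.88/-1.54/-2.41 | 0.18/0.15/0.14 | 0.46 |
| 20% v 10% | -0.04 (0.31) | 0.84/1.49/2.36 | 0.56/0.67/0.73 | 0.54 |
| 5% v 10% | 0.03 (0.33) | -0.41/-0.73/-1.16 | 0.24/0.22/0.21 | 0.48 |

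At 15% v 15% the MMRM gives -0.02 (0.32), and in a run without dropout the composites were within 0.04 of zero.

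*Hand check.* Mean W under the assumed timing is 0.3 x 0.957 + 0.2 x 0.885 + 0.1 x 0.808 + 0.2 x 0.654 + 0.1 x 0.423 + 0.1 x 0.154 = 0.733. A 10-point mortality gap then shifts the difference by 0.0733 x (D - m). The D = 21 result implies m of about 9, which predicts -1.54 at D = 30 and -2.42 at D = 42, as simulated.

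**Step 4: sensitivity.**

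- Worsening of 4 or 8 points recorded at the last visit before every death moves the MMRM to -0.27 or -0.54 (10% v 20%), or to -0.13 or -0.25 (5% v 10%). The insensitivity is large but not total.
- Over SD 5-7 at 10% v 20%, the composites stay within -0.82 to -0.94, -1.47 to -1.59 and -2.34 to -2.47.
- A separate model (correlation 0.9^lag, 1.2-point benefit, D = 42) kept the MAR difference at 1.00-1.09, while the composite ran from -1.73 (10% v 20%) to 2.37 (15% v 10%).

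**The case against.** The strongest reply is that death is already covered. The only secondary endpoint is mRS 0-2 with death carried forward and, in Protocol 7.3, its own posterior probability against 6.25%. NIHSS responder rates default to non-response, deaths are tabulated, and an independent DMC sees unblinded data. A plain death count also detects a mortality imbalance better than the proposed analyses: signal/SD at 10% v 20% is 1.5-1.6, against 0.7 for the rank analysis and 0.8/1.0/1.2 for the composites. All of this stands. It shows that an imbalance would be noticed, not what it does to the AUC result. mRS 0-2 also scores death the same as mRS 3-5, so the death of a patient who would otherwise have been dependent changes nothing there.

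Second, the absence is only of visible text. Redactions and missing pages in SAP 8.3.4 to 8.5 are where such an analysis could sit, and the MMIAS definition is not visible. This stands and limits the claim.

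Third, the composite depends on an arbitrary death score and is noisier, the rank version is on another scale, and the mortality gaps are invented. This is correct, and is why a range of scores is proposed, as a supplement only.

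Fourth, Protocol 4.2 says "subjects with more profound stroke have substantially increased risk of death and permanent disability" to explain why such patients are kept out. True; the mortality rates in the sample-size sections suffice to show that deaths were expected.

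Fifth, the study is exploratory Phase 2a, with no hypothesis tests and no visible go/no-go rule. That argues for leaving the primary analysis alone, not for leaving its meaning unstated.

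**Conclusion.** The concern holds. As written, the primary AUC difference, its interval and its posterior probability estimate a contrast in which nobody dies; Table 1 gives the method but not that meaning, and no visible AUC analysis counts death. The weights in Step 1 follow from the SAP alone. The size of the effect rests on assumed mortality, timing, SD and death scores. At 10% v 20% the gap between the two contrasts is about 0.9 to 2.4 NIHSS points, against a threshold of 0.6. At 5% v 10% it is about 0.4 to 1.2, so with death scored 21 it stays below 0.6. With equal mortality it is close to zero. This is worth fixing because it is cheap and changes what the primary result can support.

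**What to change.** 1. In Table 1, separate death from missing data and label the MMRM as the hypothetical-strategy estimate for death.
2. Before the interim database lock, when randomization is loaded (SAP 2.3), pre-specify one supplementary death-inclusive analysis, reported beside the MMRM with no new decision rule. Either (a) a composite AUC over a stated range of death scores, which keeps the units of the 0.6 threshold, or (b) a rank analysis with deaths worst, which needs no death score but is on another scale and no more sensitive.
3. The SAP defines only a group-level AUC, and SAP 2.4 foresees gaps among the living: "The number and proportion of missing assessments (due to missed visits or study drug discontinuation) will be monitored on an ongoing basis". State how a per-patient AUC is obtained for them, for example by multiple imputation under MAR with the MMRM's terms, applying death scores or ranks only from the first scheduled visit after an actual death.
4. State how patients with unknown vital status at Week 52 are treated, and report their number by arm.
5. If a redacted section already has such an analysis, cross-reference it in Table 1.

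The cost is SAP wording, one extra analysis and one imputation step. No visits are added and the primary MMRM does not change. The composite's interval is wider: with the assumed inputs at 10% v 20%, the SE is 1.12, 1.47 or 2.00 for death scores 21, 30 or 42, against about 0.92 for the MMRM. Vital status may also be unknown after withdrawal. The supplement does not replace the death table.
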